6.1 Enrollment form – Screening and Consent

All open tibias will be screened during the enrollment study of the period. All included patients will be recorded in the same project and treatment arm on REDCAP regardless of whether or not they are in the RCT or Cohort study. Even those that will be excluded need to be reported on REDCAP.

1. Add a new record
2. Record Date of Screening, MRN, and First/Middle/Last Name
 - a. MRN is to be in the format BXXXXXXX as in all MRNs need to be led by a "B" followed by the appropriate number of blank zeroes. This is to maintain consistency with the MOI EMR and Clear Canvas
 - b. The first letter of each name should be capitalized

Participant ID	
* must provide value	
Date of Screening	  
Format is DD-MM-YYYY. Insert date manually, by clicking on the calendar image above, or press "Today" if applicable.	
Medical Record Number	
* must provide value	
First Name	
* must provide value	
Middle Name	
Last Name	
* must provide value	

The next steps involve screening the patient for the appropriate inclusion/exclusion criteria. These should be performed with assistance from the patient's surgeon.

3. Fill in inclusion criteria
 - a. Question1: OTA 42 refers to diaphyseal (mid-shaft) tibia fracture which must be confirmed by radiographic imaging
 - b. Question 2: Pedal pulses palpable is a clinical finding that confirms that the patient's vascular system is intact
 - c. Question 3: Presentation time to MOI is defined as the time that they arrived at MOI's emergency room (not Muhimbili National Hospital EMD)
 - d. Question 4: Skeletal mature is defined by closed physis as seen on radiographic imaging
 - e. Question 5: Primarily closable wound means that the skin is intact and that the contamination level is low enough for the patient's wound to be fully closed at the time of surgery.

Matrix group: inc

Inclusion Criteria			
Variable: ota_42	yes	no	
Sustained diaphyseal open tibia fracture (AO/OTA 42) *must provide value			reset
Variable: inc_vasc	yes	no	
Pedal pulses palpable (vascular system is intact) *must provide value			reset
Variable: inc_24hr	yes	no	
Presentation to MOI within 24hr of injury *must provide value			reset
Variable: inc_mature	yes	no	
X-ray's confirm skeletal maturity *must provide value			reset
Variable: inc_primary	yes	no	
Wound can be primarily closed (no flap or delay in closure due to contamination needed) *must provide value			reset

4. Fill in Exclusion Criteria

- Question 1: Pathologic fracture means a fracture which is due to weakening of the bone caused by an underlying bone disorder such as a tumor or osteoporosis.
- Question 2: Bilateral (meaning both legs) tibia fractures are excluded due to the difficulty in randomizing a patient with two open fractures and also the potential negative influence on outcomes that having two tibia fractures cause
- Question 3: GCS stands for Glasgow Coma Score. It is a rapid way to assess neurologic function. GCS < 12 means impaired cognitive function.
- Question 4: Paralysis means inability to use a particular body part
- Question 5: TBSA stands for Total Body Surface Area. Burns are calculated by assessing the percent of the skin they cover.
- Question 6: Prior ipsilateral leg injury means a previous injury in the same leg
- Question 7: This question is to rule out patients with physical or function leg deformities

Matrix group: exc

Exclusion Criteria			
Variable: exc_path	Yes	No	
Current injury is a pathologic fracture *must provide value			reset
Variable: exc_bilat	yes	no	
Sustained bilateral tibia fracture *must provide value			reset
Variable: exc_femur	yes	no	
Sustained comminuted femur fracture *must provide value			reset
Variable: exc_gos	yes	no	
Sustained severe Traumatic Brain Injury (GCS< 12) *must provide value			reset
Variable: exc_spine	yes	no	
Sustained severe spinal cord injury (lower extremity paresis/paralysis) *must provide value			reset
Variable: exc_burn	yes	no	
Sustained severe burns (>10% TBSA or >5% TBSA with full thickness or circumferential injury) *must provide value			reset
Variable: exc_ipsl	yes	no	
Prior ipsilateral leg injury requiring surgery *must provide value			reset
Variable: exc_limb	yes	no	
Prior or current lower limb deformity or abnormality *must provide value			reset

At the end of answering these questions, an automated message will be generated based on the answers provided.

5. Observe automated eligibility message
 - If all inclusion criteria are answered as “yes” and all exclusion criteria are answered as “no”, the patient is eligible for the RCT
 - If the patient (1) came to MOI 24 hours after injury, (2) has a non-primarily closeable wound, or (3) came to MOI 24 hours after injury AND has a non-primarily closeable wound, the patient will be eligible for the cohort study.
 - All other responses will result in exclusion for the study.

Subject IS eligible for the RCT study.
Subject is NOT eligible for the RCT study but IS eligible for the prospective cohort follow-up study.
Subject is NOT eligible for any study.

6. In situations where a patient is excluded for a particular reason, the only information that needs to be filled out on the screening form is the patients MRN, full name, and the one reason why the patient is excluded. It is not necessary to go through the other screening criteria if one criteria for certain excludes the patient. For excluded patients, a pop up box will appear. Record the exact reason for exclusion here.

Describe the reason for exclusion <small>* must provide value</small>		<small>Expand</small>
--	----------------------	-----------------------

7. Next, record whether or not the patient consents to the study.
 - a. If there is concern that the patient will not be able to be contacted for the 1 year follow-up visit, please choose that option. Note that this is one of the exclusion criteria.
 - b. If the patient is able to attend the follow-up visits but does not agree to participate in the study for any other reason, click “No” and record the reason why. It is important to record the reason why so that the study team can identify consistent reasons for not participating in the study.
 - c. If the patient provides consent, click “Yes” and confirm the study that the patient is enrolled in. This should match the study that the system automatically calculated. If it does not match, warning messages will pop up. Double check the screening questions to make sure the patient is enrolled in the correct study
 - d. If the patient was not identified before their operation but later found to have been eligible, record “missed patient”

      Variable: consent_y/n [Branching logic exists]	
Has the patient agreed to be enrolled in the study? <small>**This is a key study question**</small> <small>* must provide value</small>	 Yes  No  Excluded because unlikely to attend all follow-up visits  Missed patient (did not catch patient before surgery)

The patient has been enrolled in the wrong study.

The patient IS eligible for the RCT but has been enrolled in the COHORT study.

Please double check the inclusion/exclusion criteria. Do not proceed until this error has been resolved.

The patient has been enrolled in the wrong study.

The patient IS eligible for the COHORT but has been enrolled in the RCT study.

Please double check the inclusion/exclusion criteria. Do not proceed until this error has been resolved.

Enrollment Form - Baseline Clinic Information

1. Record demographic information
 - a. If the exact date of birth down to the date cannot be provided, leave that field as empty and record in the text box an estimate of how old the patient is. When the patient's relatives come, please ask them for the exact date of birth
 - b. "Number of people in household" refers to the number of people the person shares a room/apartment/house with. These people may or may not be family members
 - c. "Number of people patient financially supports" refers to number of people the patient helps financially. These may or may not be family members
 - d. Insurance status refers to the type of insurance the patient has. If the patient buys insurance from a private company, check "Private". If the insurance the patient has is provided by the government, check "Public".

Demographics	
Date of Birth	    * must provide value
Gender	 Male  Female 
If the patient does not remember the date of birth, what is the patients age at time of injury (in years)	
Height (cm)	 This value is self reported
Weight (kg)	 This value is self reported
Highest level of education finished:	 None  Year 1 and 2 (Pre-Primary)  Standard I-VII (Primary)  Form 1-4 (Secondary Ordinary)  Form 5 and 6 (Secondary Advanced)  College  University 
Number of people in household (including the patient):	
Number of people patient financially supports (including the patient):	
Insurance Status	 Private  Government  None 

2. Ask about work status
 - a. “Formal Employment” refers to an official job with a contract such as a salaried health records technician at MOI. “Informal Employment” refers to people like boda boda drivers, etc.
3. Past Medical and Social History
 - a. Please individual ask the questions provided. Do not just say “do you have any other health problems”; if asked in this way, patients are more likely to forget to mention something
 - b. CD4 count refers to a lab test often given to people with HIV to check on their health status. Patients may or may not have been tested.
 - c. Smoking is a particularly important question because many studies on infection rates following open fracture repair cite smoking status as one of the contributors to an infection after surgery.

Past Medical and Social History	
Diabetes Status <small>* must provide value</small>	 Yes  No  Decline to Answer  Unknown (Never Tested)
<small>reset</small>	
Additional comorbidities <small>* must provide value</small>	 None  Heart disease  Lung disease  Kidney disease  History of stroke  Tuberculosis  Other
HIV/AIDS Status <small>* must provide value</small>	 Yes  No  Decline to Answer  Unknown (Never Tested)
<small>reset</small>	
Last known CD4 count AND DATE (if available)	

 <small>Answer only if patient has HIV/AIDS</small>
<small>Expand</small>	
Other comorbidity 	
Smoker <small>* must provide value</small>	 Current Smoker  Former Smoker  Non-Smoker
<small>reset</small>	
For how many years has the patient been smoking?	
About how many cigarettes does the patient smoke per day?	
For many years did the patient smoke?	
About how many cigarettes did the patient smoke per day when the patient was an active smoker?	
Does the patient drink alcohol?	 Yes  No
<small>reset</small>	
Number of drinks per WEEK	
<small>1 drink = 1 alcoholic beverage</small>	

4.

Past Medical and Social History	
Diabetes Status <small>* must provide value</small>	 Yes  No  Decline to Answer  Unknown (Never Tested)
<small>reset</small>	
Additional comorbidities <small>* must provide value</small>	 None  Heart disease  Lung disease  Kidney disease  History of stroke  Tuberculosis  Other
HIV/AIDS Status <small>* must provide value</small>	 Yes  No  Decline to Answer  Unknown (Never Tested)
<small>reset</small>	
Last known CD4 count AND DATE (if available)	<small>Expand</small>
<small>Answer only if patient has HIV/AIDS</small>	

5. Injury Characteristics

- a. “Date and Time of Presentation to MOI” refers to the time they arrive at MOI’s emergency room, not Muhimbili National Hospital emergency room
- b. “Outside Hospital” refers to any other hospital besides the hospitals in the Muhimbili Complex
- c. “Fall from standing height” means the patient was standing on the floor and then fell onto the floor (as in they did not fall off a roof)

Injury Characteristics		
Date and Time of Injury * must provide value	   Now D-M-Y-HM Insert date and time by clicking on the calendar image above	
Date and Time of Presentation to MOI * must provide value	   Now D-M-Y-HM Insert date and time by clicking on the calendar image above	
In which city did the injury occur?		
Was the patient referred to MOI from an outside hospital?	 Yes  No	
How much time did it take to get to a hospital after the injury?		
Did the patient go from the injury site to the hospital by ambulance?	 Yes  No	
Side of tibia fracture	 Left  Right	
Mechanism of Injury	 Road Traffic Injury  Fall  Crush Injury (heavy object falling on leg)  Gunshot  Other	
Was the patient a:	 Driver (car)  Passenger (car)  Driver (motorbike)  Passenger (motorbike)  Bicyclist  Pedestrian	
Was the fall from standing height? ("Standing height" means they were standing on the floor and fell on the floor)	 Yes  No	
How far did the patient fall? (meters)		
Describe "Other" mechanism of injury		

6. EQ-5D at Baseline

- The EQ-5D questions at this step of the study refer to the patient's health status just before the injury
- It is best to provide all the answer choices to the patient before allowing the patient to make a choice. This is how the original EQ-5D in English is tested and validated, and we should try to perform the EQ-5D as close as possible to the original way in which it was performed

EQ-5D

Tafadhalo onyesha maelezo yapi yanaelezea vizuri zaidi hali ya afya yako kwa leo.

Uwezo wa kutembea

* must provide value

- Sina tatizo katika kutembea
- Nina matatizo kiasi katika kutembea
- Siwezi kutembea kabisa

reset

Uwezo wa kujihudumia

* must provide value

- Sina tatizo kujihudumia mwenyewe
- Nina matatizo kiasi katika kujisafisha au kuva mwenyewe
- Siwezi kujisafisha wala kuva mwenyewe

reset

Shughuli za kila siku (mfano: kazi, kusoma shuleni/chuoni, kazi za nyumbani, shughuli za kifamilia au starehe)

* must provide value

- Sina tatizo katika kufanya shughuli zangu za kila siku
- Nina matatizo kiasi katika kufanya shughuli zangu za kila siku
- Siwezi kabisa kufanya shughuli zangu za kila siku

reset

Maumivu / Kutojisikia vizuri

* must provide value

- Sina maumivu au sina kutojisikia vizuri
- Nina maumivu kiasi au najisikia vibaya kiasi
- Nina maumivu makali au najisikia vibaya sana

reset

Wasiwasi / mnyong'onyeo

* must provide value

- Sina wasiwasi au mnyong'onyeo
- Nina wasiwasi kiasi au mnyong'onyeo kiasi
- Nina wasiwasi sana au nina mnyong'onyeo sana

reset

Ili kuweza kukusaidia wewe kusema kama hali yako ya kiafya ni nzuri au mbaya, tumechora kipimo kinachofanana na kipiima joto. Hali nzuri kabisa unayoweza kufikiria imewekewa alama ya 100 (mia moja) na hali mbaya kabisa unayoweza kufikiria imewekewa alama ya 0 (sifuri).

Sasa tungependa utuambie sehemu katika kipimo hiki ambapo ungiweka hali yako ya afya leo.

* must provide value

Click bar above and then drag to set response

reset

7. Contact Information

- a. We will record at minimum 3 phone numbers. The first one will most likely be the patient's own phone number. Additional phone numbers can either be other phone numbers that the patient has or friends/relatives
- b. In the "Relationship to patient" question, a text box has been provided. Enter any description that will be useful when contacting that person such as "brother in law".
- c. After collecting 3 phone numbers, call the numbers and inform the people you call of the patient's injury and of their participation in the study. Also mention the importance of helping the patient attend all follow-up clinics. This is to encourage the contacts to take part in the patient's care and help them remember to attend the clinics.

Contact Information	
Primary phone number (most preferred contact)	
* must provide value	
Contact name (write "Self" if this is the patient)	
* must provide value	
Relationship to patient (write "Self" if this is the patient)	
* must provide value	
Secondary phone number	
* must provide value	
Contact name	
* must provide value	
Relationship to patient	
* must provide value	
Third phone number	
* must provide value	
Contact name	
* must provide value	
Relationship to patient	
* must provide value	
Were all three phone numbers successfully test called?	 Yes  No
* must provide value	
reset	
Save this form as "Incomplete" until you are able to successfully test call all 3 numbers.	

8. Additional contact

- a. In situations where there is concern that the patient may be lost to follow-up, record additional phone numbers as back-up.
- b. "Describe where you live" is a free text box. Provide as much detail as possible so that it may be possible to find the patient later on if the phone numbers no longer work and they are lost to follow-up.

Additional Numbers	
Ward leader phone number (if available)	
Ward leader name	
Record additional phone numbers here. For each number, include the following:	

 - Number - Name - Relationship (Self, Family, Friend, or Other) 	Expand

Address

Describe where you live:

Expand

Describe where you plan to spend most of your time during recovery

Expand

Email

E-mail

If available

9. Antibiotics

- a. Once the patient has provided consent to participate in the study, they should receive antibiotics as quickly as possible if they have not yet.
- b. If the patient received antibiotics at another hospital but then came to MOI and was changed onto a study antibiotic regimen, choose "other" and record the details of all antibiotics given since the time of injury

Antibiotics

Date and time of first dose of antibiotics administered after the injury

* must provide value

Now D-M-Y H:M

Insert date and time by clicking on the calendar image above

Was the first dose of antibiotics administered at MOI?

* must provide value

Yes

No

reset

What antibiotic regimen is the patient starting on at MOI?

* must provide value

Ceftriaxone only

Ceftriaxone + gentamycin

Ceftriaxone + gentamycin + metronidazole

Other

reset

If "Other", describe the following:

- Type of antibiotic
- Dosage
- Length of administration
- Reason of using a non-standard antibiotic

Expand

Standard Study Antibiotics Regimen

- None or Mild Contamination: Ceftriaxone (1g every 24hr for 2 days)
- Surface Contamination (not ground in): Ceftriaxone (as above) + Gentamycin (80mg every 12hr for 2 days)
- Severe or High-Risk: Ceftriaxone + Gentamycin (as above) + Metronidazole (500mg every 8hr for 2 days)

10. Tetanus prophylaxis

- a. All patients should have tetanus prophylaxis. This is usually in the form of a shot given in childhood with repeated shots every few years. If the patient does not remember or knows they have never received a tetanus shot, work with the National Hospital Emergency physicians to ensure the patients get the shot as soon as possible. This is most important for the patient's health, but also important for the study.
- b. Ward number refers to the ward that the patient will be sent to after the operation. This depends on the patient's insurance status.

Tetanus Prophylaxis		
Has the patient received tetanus immunization (either in the past or now)?		
 Yes  No  Unknown		
reset		
Please check the patient's file or tell the physician to administer tetanus immunization		
Ward Number		
Which ward is the patient expected to go to after the operation? 		

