By placing a tick in one box in each group below, please indicate which statements best describe your own health state today.

Mobility

I have no problems in walking about

I have some problems in walking about

I am confined to bed

Self-Care

I have no problems with self-care

I have some problems washing or dressing myself

I am unable to wash or dress myself

Usual Activities (e.g. work, study, housework, family or leisure activities)

I have no problems with performing my usual activities

I have some problems with performing my usual activities

I am unable to perform my usual activities

Pain / Discomfort

I have no pain or discomfort

I have moderate pain or discomfort

I have extreme pain or discomfort

Anxiety / Depression

I am not anxious or depressed

I am moderately anxious or depressed

[figure not shown]
I am extremely anxious or depressed

To help people say how good or bad a health state is, we have drawn a scale (rather like a thermometer) on which the best state you can imagine is marked 100 and the worst state you can imagine is marked 0.

We would like you to indicate on this scale how good or bad your own health is today, in your opinion. Please do this by drawing a line from the box below to whichever point on the scale indicates how good or bad your health state is today.

Your own health state today

Best imaginable health state

Worst imaginable health state

UCSF-MOI Open Tibia Fracture Study – OTA Wound Classification

As part of the study, we are collecting data on the types of wounds that our study participants have. Please fill out this handout after the operation. Leave it in the patient's file after you have filled it out. If you have any questions, please contact the study phone at [name].

Patient Name: _____ MRN: _____

Wound measurement (take the maximum length): _____ cm

Skin	 Laceration with edges that approximate  Laceration with edges that DO NOT approximate  Laceration associated with extensive degloving
Muscle	 No muscle necrosis OR some injury with function intact  Loss of muscle but remains functional OR localized necrosis in injured area that requires excision  Dead muscle, loss of function, partial or complete compartment excision, complete disruption disruption of muscle-tendon unit, muscle injury not approximatable

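### The baseline EQ-5D is meant to describe health just before the injury, but the form shown asks about health today, so the recorded baseline may mix pre-injury and acute-injury states

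*Protocol*

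**What the plan says.** The intended time frame is in Protocol Section 6.1, item 6 (EQ-5D at Baseline): "The EQ-5D questions at this step of the study refer to the patient's health status just before the injury". The next bullet asks staff to offer all answer choices before the patient chooses, and gives as its reason that "we should try to perform the EQ-5D as close as possible to the original way in which it was performed".

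The form reproduced directly below asks about something else. Its Swahili stem reads "onyesha maelezo yapi yanaelezea vizuri zaidi hali ya afya yako kwa leo", where *kwa leo* means for today. The 0-100 scale prompt reads "Sasa tungependa utuambie sehemu katika kipimo hiki ambapo ungiweka hali yako ya afya leo", where *leo* again means today.

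The English EQ-5D in the Appendix uses the same frame in both parts: "please indicate which statements best describe your own health state today" and "We would like you to indicate on this scale how good or bad your own health is today, in your opinion".

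On timing, Section 5.1 has the coordinator collect baseline information once consent is complete. Section 5.6 places randomisation after debridement and the check that the wound can be closed. Section 4.1 lists EQ-5D health-related quality of life as a secondary functional outcome, and Section 3 names quality of life in Aims 2 and 3.

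**The concern.** The manual and the form give the same question two reference periods. For a stable condition that would hardly matter. Here the patient has just sustained an open tibial shaft fracture, and the two periods fall on either side of it. On the Swahili mobility item, the same patient could truthfully choose the best level for just before the injury and the worst level for today. Self-care, usual activities and pain could move in the same direction.

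The instruction reaches the coordinator who reads the manual; the printed words are what the patient hears or reads. The protocol shows no baseline version of the stem, no replacement script, and no field recording which period was used. Section 5.10 has coordinators hand over duty every three days, so the override has to be made by several people, each time.

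At stake is whether baseline EQ-5D can be read as pre-injury health. If it cannot, a comparison of one-year scores with the pre-injury level loses its anchor, and baseline EQ-5D becomes a noisier covariate. A statistical analysis plan cannot recover this, because the ambiguity enters when the question is asked.

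**Working it through.** **Texts side by side**

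| Source in the protocol | Time frame |
|---|---|
| Section 6.1, item 6, instruction to staff | just before the injury |
| Section 6.1, baseline form, Swahili stem | today |
| Section 6.1, baseline form, Swahili 0-100 scale | today |
| Appendix, English EQ-5D, descriptive part | today |
| Appendix, English EQ-5D, 0-100 scale | today |

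The staff instruction is the only item with the pre-injury frame. The English form carries no visit label, and today is correct at follow-up, so it is supporting evidence only. The contradiction rests on the Swahili form, which sits in the baseline section under the instruction it conflicts with.

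**Does it reach the treatment comparison?** The planned order is consent, baseline, debridement and closure check, randomisation. The baseline answer is given before the arm is known, so the error should have the same distribution in both arms. A between-arm comparison of follow-up EQ-5D is therefore not biased by it. Reoperation does not use the EQ-5D. The protocol's only sample-size figure, 88 per group, is for reoperation and does not enter here.

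**Size.** The documents give no EQ-5D value set, standard deviation or expected score, so the following only illustrates. All three inputs are assumptions:

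- q, the share of patients answering for today: 0.10 to 0.50
- D, the gap between pre-injury and acute index scores, taken as constant: 0.3 to 0.7
- s, the true pre-injury standard deviation: 0.1 to 0.2

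Formulas:

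- shift in the baseline mean = −qD
- baseline variance = s² + q(1 − q)D²
- factor on the baseline to follow-up correlation = s / √(s² + q(1 − q)D²), if the frame a patient used is unrelated to pre-injury health and to the follow-up score

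Mild corner (q = 0.10, D = 0.3, s = 0.2): shift = −0.03; variance = 0.04 + 0.09 × 0.09 = 0.0481; SD = 0.219, or 1.10 times s; correlation factor 0.91.

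Middle (q = 0.25, D = 0.5, s = 0.2): shift = −0.125; variance = 0.04 + 0.1875 × 0.25 = 0.0869; SD = 0.295, or 1.47 times s; correlation factor 0.68.

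Severe corner (q = 0.50, D = 0.7, s = 0.1): shift = −0.35; variance = 0.01 + 0.25 × 0.49 = 0.1325; SD = 0.364, or 3.64 times s; correlation factor 0.27.

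The two ends matter as well. With q = 0 (every coordinator overrides the form) there is no error. With q = 1 (everyone reads it as printed) nothing is mixed, but the whole baseline describes the acute injury and its mean is off by D. Nothing on the form tells these cases apart.

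**The case against.** The strongest reply is that the plan has already fixed the time frame. The instruction is explicit, it is the first bullet above the form, coordinators ask the questions themselves, and Section 4.3 schedules training before enrolment. On that view only the form text lags behind a clear intention. This stands as far as intention goes. It does not show that the intention reaches the patient, since no wording is supplied to carry it.

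Three stronger readings are tempting, and the documents do not support them.

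- A reader might infer that the baseline certainly mixes two states. Nothing in the protocol shows how any coordinator put the question; mixing is a risk, not an established fact.
- A reader might take the request to stay close to the original administration as an order to read the form verbatim. In context it concerns offering all answer choices first, and the bullet before it changes the reference period. It offers no help with rewording, but it does not order the printed stem to be read out.
- A reader might infer that the treatment effect on quality of life is compromised. Baseline is planned before randomisation, and the protocol states neither a change-from-baseline nor a baseline-adjusted EQ-5D analysis. In Aim 3 quality of life is a target of the prognostic work; baseline EQ-5D is not named as a predictor. Harm through those uses depends on an analysis plan that is not shown.

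**Conclusion.** The contradiction is real and visible on the page: the manual asks for pre-injury health, and the baseline form asks about today in both of its parts. The baseline may therefore mix pre-injury and acute-injury states, or record the acute state throughout, and the data would not show which.

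The consequence is limited. The randomised comparison of follow-up EQ-5D and the reoperation outcome are unaffected, provided baseline is collected before randomisation as planned. What is undermined is the description of pre-injury quality of life and, only if the analysis uses it that way, baseline EQ-5D as a reference for recovery or as a covariate. On the assumed inputs the baseline mean falls by 0.03 to 0.35, and the correlation with follow-up is multiplied by 0.91 down to 0.27. None of those inputs comes from the documents, so the range shows that the effect can be material, not how large it is. The point is worth correcting because the remedy is small and follows the plan's own intention.

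**What to change.** On the baseline form, change the stem of the five questions and the 0-100 scale prompt to ask about health just before the injury, in Swahili and English, in REDCap and on paper. Keep today on the forms for follow-up visits.

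For patients already enrolled, flag the baseline EQ-5D as collected under the today wording with the time frame uncertain. The form never captured which period was used, so it should not be filled in afterwards from memory. Wherever baseline EQ-5D is used, add a sensitivity analysis without the flagged records. If the form changes only after enrolment has ended, every record is flagged and this becomes an analysis without baseline EQ-5D.

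The cost is two sentences in two languages and a short notice to coordinators. The April 2016 entries in Section 1 show that the team has already edited a REDCap question mid-study when its wording was thought to distort the data, so the route exists. The one drawback is that a recalled stem departs slightly from the standard questionnaire, which the plan already accepts by asking for pre-injury health.
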